The study population is preschool children attending kindergartens in different districts in Hong Kong. It is planned to recruit around 10 kindergartens. All children attending grade 1 in these kindergarten will be invited to receive a free dental examination and have their decayed primary teeth restored, if possible, in the kindergarten by dentists. Parental informed consent will be obtained before the dental examination and treatment. The planned sample size is 152 children with 396 decayed primary teeth needing restorations. Around half of these teeth, assigned randomly will received SDF treatment around 10 weeks before receiving the restoration. The restored teeth will be re-examined every 6 months for 24 months to assess the treatment outcome. Parents of the study children will be asked to complete a questionnaire at baseline, 6 months and 24 months so as to obtain data on their satisfaction with the aesthetics of their child's teeth and the oral health-related quality of life of the study children.

Background

Dental caries of young children is common in both developing and industrialized countries (Petersen et al., 2016). In Hong Kong, the prevalence of dental caries among 5-year-old children is around 50% (Department of Health, 2013). The adverse effects of dental caries can impact on both children and their families, including significant health, social and economic consequences (Colak et al., 2013).

Previous studies have shown that topical application silver diamine fluoride (SDF) solution is effective in arresting dental caries in young children (Chu et al., 2002; Yee et al., 2009; Zhi et al., 2012; Duangthip et al., 2016). A considerable drawback of SDF application is the black stain on the arrested caries lesions, which may cause dissatisfaction of both children and their parents with aesthetics of the treated teeth (Gao et al., 2016). It was suggested that by applying a saturated solution of potassium iodide (KI) immediately after the application of SDF, would minimize the black stain on the dentin caries lesions (Knight et al., 2006). However, a long term clinical study on elders has shown that the application of KI cannot reduce the blackening of arrested dentine caries lesions from SDF treatment (Li et al., 2016).

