At baseline, information on the children's oral hygiene practice, snacking habit, oral health related quality of life, and parental satisfaction with the appearance of their child's teeth will be collected by a self-completed questionnaire. A validated tool for measuring oral health related quality of life of preschool children in Hong Kong, Chinese version of Early Childhood Oral Health Impact Scale (ECOHIS), will be used (Lee et al., 2009). The same measurement tool will be used at the 6-month and 24-month follow-up.

Primary outcome measure

The primary outcome measure in this clinical study is the success of the ART restorations placed. A restoration is classified as success when it is retained on the tooth without major defects or wear and has no associated active caries (codes 0 and 1). Under this condition, no further treatment is necessary. A restoration is classified as failed when it has major defects (codes 2 and 3), associated active caries (code 4), is missing (codes 5 and 6) or the tooth has signs of pulpal pathology (code 7) or extracted due to caries (code 8). Under these conditions, further treatment may be necessary.

Secondary outcome measures

The secondary outcome measures in this clinical study are the parental satisfaction with aesthetics of their child's teeth and the oral health related quality of life of the child as measured by the ECOHIS before and after placement of ART restorations.

Data analysis

The clinical examination record form and parental questionnaires will first be checked for completeness and obvious errors. Questionnaires with more than 40% of the questions unanswered will be discarded. The collected data will be entered into computer. Data entry and logical errors will be corrected before data analysis.

Basic data analysis will be carried out by using the statistical software SPSS for Windows. Chi-square test and t-test will be performed to assess the comparability between the children in the two study groups regarding their demographic background, oral health related behaviours and baseline dental caries experience. McNemar's test and paired t-test will be used to assess the change in parental satisfaction with aesthetics of their child's teeth and the change in ECOHIS score before and after placement of ART restorations.

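### The 40% blank-question rule is applied to the whole parental questionnaire, so it can discard an answered secondary outcome because of blanks elsewhere on the form

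*Protocol*

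**What the plan says.** The protocol's section on baseline and follow-up data collection describes one baseline form for parents. It lists "information on the children's oral hygiene practice, snacking habit, oral health related quality of life, and parental satisfaction with the appearance of their child's teeth" and says that this "will be collected by a self-completed questionnaire". ECOHIS is the instrument for quality of life. For later visits the section adds: "The same measurement tool will be used at the 6-month and 24-month follow-up". The Summary says that parents complete a questionnaire at baseline, 6 months and 24 months, in order to "obtain data on their satisfaction with the aesthetics of their child's teeth and the oral health-related quality of life of the study children". It does not mention hygiene or snacking there.

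There are two secondary outcomes: parental satisfaction with aesthetics, and "oral health related quality of life of the child as measured by the ECOHIS before and after placement of ART restorations". Under Data analysis, their change is to be examined with McNemar's test and a paired t-test.

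The same section opens with data cleaning. Forms are first checked, then comes the rule "Questionnaires with more than 40% of the questions unanswered will be discarded", and only after that does the text turn to data entry. No completeness rule is given for ECOHIS or for the satisfaction question alone. The protocol states neither the number of ECOHIS items nor the length of the form.

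**The concern.** The two secondary outcomes are analysed separately, but whether either can be used depends on one count of blanks across every topic on the form. Questions about tooth-brushing or snacks can therefore decide whether a complete ECOHIS survives, and a blank ECOHIS can remove a perfectly good satisfaction answer. Because the discard comes before data entry, a scoring rule written later may have nothing left to recover.

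What is at stake is pairs. The before/after tests need both visits, so a discarded baseline form removes that child from both the 6-month and the 24-month comparison, for both outcomes. With 152 children planned, each such form costs 1/152, or about 0.7%, of the largest possible number of pairs at each follow-up.

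**Working it through.** The 40% limit is a rule, not a computed figure, so there is nothing to reproduce. The check is what the rule does to each outcome.

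**Inputs.** From the protocol: the 40% limit, counted over all questions; a baseline form with four topics; two secondary outcomes. Not in the protocol, so assumed: E ECOHIS items (10 to 20) and o other questions. Then T = E + o and s = E/T. A form is discarded when its blanks exceed 0.4T.

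**1. Losing a complete ECOHIS.** All blanks lie outside ECOHIS, so the most there can be is o.
- Condition: o > 0.4(E + o), so o > 2E/3, which is s < 60%.
- At the threshold every other question, including satisfaction, must be blank. In general more than 0.40/(1 − s) of the other questions must be blank: 80% at s = 50%, 67% at s = 40%.

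**2. Losing an answered satisfaction item.** Suppose ECOHIS is blank and everything else is answered, so there are E blanks.
- Condition: E > 0.4(E + o), so o < 1.5E, which is s > 40%.

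| Assumed E | Complete ECOHIS can be lost from o = | Answered satisfaction item can be lost up to o = |
|---|---|---|
| 10 | 7 | 14 |
| 13 | 9 | 19 |
| 16 | 11 | 23 |
| 20 | 14 | 29 |

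Check at E = 13:
- o = 9 gives T = 22 and a limit of 8.8, so 9 blanks (41%) are discarded.
- o = 19 gives T = 32 and a limit of 12.8, so 13 blank ECOHIS items (41%) are discarded.
- o = 20 gives T = 33 and a limit of 13.2, so 13 blanks (39%) are kept.

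**3. Whether the item counts matter.** Every s is below 60%, above 40%, or both. So on any form that carries both outcomes, at least one of the two losses is possible. Between 40% and 60% both are. The unstated counts decide which outcome is exposed, not whether one is.

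**4. What a kept form guarantees.** If all the blanks fall in ECOHIS, the largest blank share of ECOHIS on a kept form is min(100%, 40%/s), before rounding to whole questions:

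| s | 40% or less | 50% | 60% | 80% | 100% |
|---|---|---|---|---|---|
| Largest ECOHIS share blank | 100% | 80% | 67% | 50% | 40% |

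For example, with E = 13 and o = 12, 10 blank ECOHIS items out of 25 questions is exactly 40%. That does not exceed the limit, so the form is kept with 10/13 = 77% of ECOHIS missing. With o = 4 the most is 6 of 13 (46%).

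**The case against.** **The rule is only a floor for data entry.** Nothing says that a kept form must yield an ECOHIS score. How a partly blank ECOHIS is scored is commonly left to the SAP, which is not shown. This stands for kept forms: section 4 of the working shows that the rule does not ensure completeness, not that poor scores will be analysed. It does not answer the discard, which is a stated rule applied before entry.

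**A reader might infer that the rule distorts the paired ECOHIS change.** The documents do not support that. It would need a score summed over answered items without adjustment, or blanks related to the outcome or differing between visits. The protocol states none of these. A wholly blank ECOHIS gives no score and no pair, so it cannot bias the t-test. Bias remains possible, but its size cannot be computed.

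**The follow-up form may be shorter.** Hygiene and snacking are named only at baseline. If the later form is ECOHIS plus a few satisfaction questions, the rule acts there almost as a limit on ECOHIS itself, and the loss of a complete ECOHIS is largely confined to baseline. That is fair. However, such a form has s well above 40%, so the exposed outcome becomes satisfaction.

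**The triggering pattern may be rare.** A parent who skips only the habit questions is caught only if those questions alone exceed 40% of the form. This stands, and no frequency can be given.

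**Materiality.** Objectives 4 and 5 are descriptive. This stands and limits the weight of the point.

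**Conclusion.** The point holds as a minor one. A completeness rule set on the whole multi-topic form can discard a fully answered ECOHIS (s below 60%, the rest blank) or an answered satisfaction item (s above 40%, ECOHIS blank), and at least one of these is possible whatever the mix of questions. It also does not by itself ensure adequate ECOHIS completeness on kept forms.

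The consequence is an avoidable loss of pairs in the secondary before/after analyses. This conclusion rests on reading the rule literally, with all questions as the denominator and the discard preceding data entry. Which outcome is exposed depends on item counts that the protocol does not give, and the number of forms affected is unknown. The primary outcome, the sample size and the comparison of restorations between groups are unaffected.

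**What to change.** Replace the whole-form rule under Data analysis with one applied separately to each secondary outcome:
- Judge ECOHIS at each visit on its own items, using either the existing 40% limit or another limit set in advance.
- Use the satisfaction answer whenever it is given.
- Do not discard one outcome because of blanks elsewhere on the form.

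With the 40% limit applied to ECOHIS alone, a usable ECOHIS could have at most 4 of 10, 5 of 13, 6 of 16 or 8 of 20 items blank, and no complete ECOHIS could be lost. The choice of limit is the sponsor's; the documents give no basis for a particular stricter one.

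The cost is about one sentence of text. Some partly completed forms must be entered that would otherwise be set aside, and the number of pairs may differ between the two outcomes, so each analysis should report its own.
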